1.1.5 Exploratory Biomarker Objectives

The exploratory biomarker objectives for this study are to identify biomarkers that are predictive of response to ranibizumab, are associated with progression to a more severe disease state, are associated with susceptibility to developing AEs, can provide evidence of ranibizumab activity, or can increase the knowledge and understanding of disease biology, on the basis of the following endpoints:

- Correlation between concentration of free VEGF (VEGF not in complex with ranibizumab) in aqueous humor at baseline and over time with PK and/or efficacy endpoints
- Correlation between concentration of free VEGF in aqueous humor at baseline and over time with DR progression
- Relationship between genetic variants (such as polymorphisms within the VEGF-A genetic locus) with the disease characteristics and/or response to treatment with ranibizumab
- Relationship between baseline imaging features and response to treatment with ranibizumab or other efficacy endpoints over time
- Relationship between baseline imaging features and DR progression

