In the event a patient's fellow eye (non-study eye) requires treatment for DR starting from the screening visit, the fellow eye may be treated per standard of care in accordance with local regulations. If the Investigator chooses to treat the fellow eye with ranibizumab, the Sponsor will provide ranibizumab 0.3 mg as per local label and regulations starting from the screening visit. Study eye treatment and fellow eye treatment may be administered at the same study visit. However, all study eye assessments and study eye treatment should be completed per Protocol first, followed by treatment in the fellow eye.

1.2.1 Treatment Assignment and Masking

Patients will be randomly allocated to one of the two study arms in a 5:3 ratio so that approximately 100 patients (PDS arm) will receive the PDS implant with ranibizumab 100 mg/mL and Q36W refill-exchange procedures, and approximately 60 patients will be assigned to the comparator arm. Randomization will be performed through the IxRS. After randomization and at each study treatment visit, the IxRS will assign the appropriate study treatment kit to be used.

Randomization will be stratified by the following baseline factors:

- Baseline ETDRS-DRSS level (47 vs. 53) as assessed by a central reading center
- Intraretinal or subretinal fluid status on SD-OCT (present vs. absent) as assessed at baseline by a central reading center

A stratified permuted-block randomization scheme will be used to obtain approximately a 5:3 ratio between the treatment groups overall and within each of the randomization strata. For analyses, the stratification factors as recorded in IxRS will be used.

Patients and study site personnel (except the BCVA examiner) will not be masked with regard to patient assignment to the PDS arm or the comparator arm because of the difficulties of maintaining masking following the surgical procedure. The Sponsor will require that the following steps be implemented as a best attempt to mask visual acuity (VA) examiners in order to minimize bias in VA assessments.

- The VA examiner will only conduct refraction and VA assessments and will be masked as best as possible to patient study eye assignment, study visit type, and patient treatment assignment.
- The VA examiner will have no access to a patient's BCVA scores from previous visits and will be aware only of the patient's refraction data from previous visits.
- The VA examiner may provide no other direct or indirect patient care.

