2.1 MULTIPLICITY ADJUSTMENT

A fixed sequence testing procedure (Westfall and Krishen 2001) will be used to control the overall type I error for the primary and the key secondary endpoints. The primary and key secondary endpoints will be tested in the order shown below at a two-sided 0.0496 significance level, proceeding sequentially starting from the primary endpoint and testing each after achieving statistical significance on the previous endpoint. The sequence for endpoint testing will be the primary endpoint, followed by key secondary endpoints in the following manner:

- 1. Proportion of patients with a ≥ 2-step improvement from baseline on the ETDRS-DRSS at Week 52
- 2. Rate of patients developing a vision-threatening complication (defined as PDR or ASNV) or CI-DME (defined as CST ≥ 325 µm) through Week 52
- 3. Rate of patients developing PDR or ASNV through Week 52
- 4. Rate of patients developing CI-DME (defined as CST ≥ 325 μm) through Week 52
- 5. Rate of patients developing ≥ 2-step worsening from baseline on the ETDRS-DRSS through Week 52
- 6. Proportion of patients with ≥ 3-step improvement from baseline on the ETDRS-DRSS at Week 52
- 7. Rate of patients developing ≥ 3-step worsening from baseline on the ETDRS-DRSS through Week 52

3. SAMPLE SIZE DETERMINATION

Patients will be randomly allocated in a 5:3 ratio to the PDS arm or the comparator arm.

The primary endpoint is the proportion of patients with a \geq 2-step improvement from baseline on the ETDRS-DRSS at Week 52.

A sample size of 160 patients randomized in a 5:3 ratio (n=100 in the PDS arm and n=60 in the comparator arm) will provide over 99% power to detect an absolute difference of 35% between arms in proportion of patients with a \geq 2-step improvement

on ETDRS-DRSS at Week 52 under the following assumptions, and to provide adequate data for assessment of key secondary endpoints:

- An achievement of a ≥ 2-step improvement on the ETDRS-DRSS at Week 52 in 15% of patients in the comparator arm (Eylea® U.S. Package Insert; Brown et al. 2021)
- Fisher's exact test
- A 4.96% two-sided type I error rate (after adjustment for planned interim data reviews conducted by the iDMC prior to analysis of the primary efficacy endpoint; see Section 1.2.2)
- A 15% dropout rate by Week 52.

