Aqueous Humor Biomarker Evaluable Population	All patients who are randomized and receive study treatment, including patients randomized to the comparator arm under observation, and have at least one optional aqueous humor sample available. Patients who receive the PDS implant insertion at any other times besides Week 4, 8, 64 or 68 will be excluded from this population. Patients who receive PDS implant insertion at Week 4 or 8 will be grouped in the PDS arm. Patients who receive PDS implant insertion at Week 64 or 68 will be grouped in the comparator arm.

ITT = intent-to-treat; PDS = Port Delivery System with ranibizumab; PK = pharmacokinetic

5. STATISTICAL ANALYSES

The primary analysis will be performed when all patients have completed the Week 52 follow up, or have discontinued from the study prior to Week 52, all data collected through Week 52 are in the database, and the data have been cleaned and verified.

Additional analyses may be performed to support the requirements of health authorities relative to marketing applications, as appropriate.

The final analysis will be performed when all patients have either completed the study (the end of which is determined at the Sponsor's discretion, depending on health authority approval of the PDS for the DR indication and Sponsor decision) or discontinued early from the study, all data from the study are in the database, and the database is locked.

Results from the primary analysis, summarized by treatment group, may be reported to the public before completion of the study.

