5.1 GENERAL CONSIDERATION

Efficacy analyses will be based on the intent-to-treat (ITT) Population unless otherwise specified.

Descriptive summaries will include the mean, standard deviation (SD), median, and range for continuous variables, and counts and percentages for categorical variables. Missing data for descriptive summaries will not be imputed unless otherwise noted.

For all efficacy endpoints, comparative efficacy analyses will be performed during the comparator-controlled treatment period (randomization through Week 60). At the primary

analysis, only the efficacy assessments collected through Week 52 will be included in the comparative efficacy analyses and descriptive summaries. At the final (end of study) analysis only the efficacy assessments collected through Week 60 will be included in the comparative efficacy analyses and data collected through end of study will be included in summaries. For the safety summaries, only data reported through Week 52 will be included at the time of the primary analysis. At the time of the final analysis, safety summaries will include all safety data collected through end of study (see Section 5.6).

Unless otherwise noted, analyses of efficacy outcome measures will be stratified by the randomization stratification factors (ETDRS-DRSS level [47 vs. 53] and intraretinal or subretinal fluid status on SD-OCT [present vs. absent] as assessed at baseline by a central reading center) as recorded in IxRS.

A nominal type I error penalty of 0.0001 (two-sided) will be taken for each time the iDMC conducts an unmasked interim safety review prior to the primary analysis. At the time of the primary analysis, four interim data reviews have been conducted by the iDMC; therefore, efficacy analyses will be performed at a significance level of 0.0496. All CIs will be two-sided and at the 95.04% level.

The occurrence of each type of intercurrent event as defined in Section 5.3.1 will be summarized by treatment arm. Additionally, the occurrence of each type of intercurrent event due to coronavirus disease of 2019 (COVID-19) as defined in the supplementary analysis in Section 5.3.3 will be summarized by treatment arm.

Data collected in selected scheduled and unscheduled visits will be mapped to visits that appear in the schedule of assessments (see Appendix 1 of the Protocol) per the Protocol using the actual study day of assessment.

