- Discontinuing study treatment (PDS arm) or discontinuing study (comparator arm) due to lack of efficacy per Investigator's judgment: A treatment policy strategy will be applied where all observed values will be used regardless of the occurrence of the intercurrent event.
- Population-level summary: Difference in adjusted mean between PDS and comparator arms grouped as assigned at randomization

All observed data will be included in the analysis regardless of whether or not a patient has experienced an intercurrent event. Missing data will be implicitly imputed by the MMRM model, assuming a missing-at-random (MAR) mechanism. The dependent variable in the MMRM model is the change from baseline in BCVA at post-baseline visits and the independent variables are the treatment group, time, treatment-by-time interaction, baseline BCVA letter score (continuous), and the randomization stratification factors of baseline ETDRS-DRSS level (47 vs. 53) and baseline intraretinal or subretinal fluid status (present vs. absent) as fixed effects. The MMRM model will assume an unstructured covariance structure. If there are convergence problems with the model, the following covariance structures will be implemented in order until convergence is achieved: first order antedependence, heterogeneous Toeplitz and first order autoregressive.

5.4.2.9 Proportion of Patients Who Lose < 15, < 10 and < 5 Letters in BCVA from Baseline over Time

The proportion of patients who lose < 15, < 10 and < 5 letters (defined as change from baseline > -15, > -10, > -5 letters respectively) in BCVA from baseline over time will be summarized comparatively through Week 52, and through Week 60, and descriptively through end of study. The analysis will use an unadjusted normal approximation for binomial proportions.

5.4.2.10 Proportion of Patients with a BCVA Score of 69 Letters (20/40 Approximate Snellen Equivalent) or Better over Time

The proportion of patients with a BCVA score of 69 letters (20/40 approximate Snellen equivalent) or better over time will be summarized comparatively through Week 52, and through Week 60, and descriptively through end of study. The analysis will use an unadjusted normal approximation for binomial proportions.

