 - b) PDS patients who were ADA positive at the reference visit and ADA titer increased after implant; in this case, the titer results of one or more samples collected after implant are at least 0.60 titer units greater than the titer result of the reference visit sample. These patients are considered to have treatmentenhanced ADA responses.

The combined rates described in (a) and (b) above will provide the incidence of patients positive for treatment-emergent ADAs. Patients are considered to be negative for Treatment-emergent ADAs if they are ADA negative at all timepoints after the reference visit. Patients are also considered to be Treatment unaffected for ADAs if they are ADA positive at the reference visit and (a) where all post-baseline titer results are less than 0.60 t.u. greater than the titer result of the reference visit, OR (b) where all post-baseline results are negative or missing. A listing of patients with positive serum antibodies to ranibizumab will be provided.

The immunogenicity assessment will also include testing for the presence of neutralizing antibodies in samples confirmed to be positive for anti-ranibizumab antibodies. The incidence of neutralizing antibodies will be grouped and reported in a similar fashion to that described above.

The relationship between ADA status and safety, efficacy, PK, and biomarker endpoints may be explored.

5.7.5 Biomarker Analyses

Biomarker analyses will be performed on the Aqueous Humor Biomarker Evaluable Population at the time of the Final Analysis. No biomarker analyses are planned at the Primary Analysis. Descriptive summaries of aqueous humor free VEGF concentration (original and log-transformed) and change in concentration from baseline will be tabulated and plotted by visit and by treatment arm.

The mean change from baseline in Free-VEGF log concentrations in the PDS arm at week W28 will be presented with a 95% CI.

The difference in the mean change from baseline in Free-VEGF fold change at W28/W24 between PDS and comparator arms respectively will be presented with a 95% CI.

Data after PDS implant from patients in the Aqueous Humor PK Population in patients with at least one post-implant Aqueous Humor PK sample will be summarized descriptively by treatment arm and overall.

Sensitivity analysis may be performed with the population that excludes patients who receive supplemental treatment.

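### The between-arm free-VEGF comparison names no adjustment for baseline free VEGF, which would narrow its interval if follow-up values correlate weakly or moderately with baseline

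*SAP*

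**What the plan says.** The between-arm estimate in SAP section 5.7.5 is "The difference in the mean change from baseline in Free-VEGF fold change at W28/W24 between PDS and comparator arms respectively". The sentence closes with "between PDS and comparator arms respectively will be presented with a 95% CI". It names no model, covariate or interval method. The sentence before it summarises the PDS arm alone, on log concentrations.

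No other section fills the gap:

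- Section 5.1 has a general rule, "Unless otherwise noted, analyses of efficacy outcome measures will be stratified by the randomization stratification factors", but it covers efficacy outcomes and does not mention biomarkers.
- Section 5.4.2.8 specifies a mixed model for visual acuity whose covariates include "baseline BCVA letter score (continuous), and the randomization stratification factors of baseline ETDRS-DRSS level (47 vs. 53") and baseline fluid status. By cross-reference the same model serves CST and macular volume (5.4.2.11, 5.4.2.12) and the exploratory non-perfusion areas (5.5.1). It is not extended to free VEGF.
- Table 1 in section 4 limits the biomarker population to patients who "have at least one optional aqueous humor sample available". It drops patients implanted at times other than four listed weeks and groups the others by implant timing. It gives no expected number.

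Baseline free VEGF is available: section 1.1.5 lists it among the biomarker endpoints, and 5.7.5 needs it to form the change. Section 1.1.5 also sets the status: "The exploratory biomarker objectives for this study are to identify biomarkers that are predictive of response to ranibizumab". Section 5.7.5 defers the biomarker work to the final analysis and attaches no test or significance level.

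**The concern.** A difference in mean change subtracts the whole baseline value from each patient's follow-up value. Unless follow-up tracks baseline closely, this adds baseline noise to the outcome. Using baseline as a covariate removes only as much of it as the data support. The cost of leaving it out is precision in the only between-arm biomarker estimate the SAP plans.

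There is a second, smaller cost. If the sampled arms differ by chance in baseline free VEGF, a change score over-corrects for that difference, because regression to the mean is counted as treatment effect. Optional sampling means that the stratified randomization does not by itself guarantee balance within the subset.

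The omission also sits oddly with the rest of the plan. The SAP speaks of adjusted means where it intends a model, and applies that model even to an exploratory continuous endpoint (5.5.1).

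**Working it through.** **Plan's own figure.** The SAP states no precision, standard deviation, correlation or sample size for free VEGF, so there is nothing to reproduce for this estimate. Its one computed design figure is 99.1% power for the primary endpoint. With 15% dropout (100 × 0.85 = 85 and 60 × 0.85 = 51), 50% against 15% and alpha 0.0496, exact Fisher power is 99.12%. That agrees, but has no bearing on the free-VEGF interval.

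**Inputs.** Allocation is from section 3: "A sample size of 160 patients randomized in a 5:3 ratio (n=100 in the PDS arm and n=60 in the comparator arm"). The total of 160 is the ceiling for the subset. The correlation rho and the subset size N are assumptions, shown over a range.

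**Large-sample variance.** Let baseline and follow-up have equal variance s² and correlation rho in both arms, on the analysis scale.

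- Change score: variance per patient 2s²(1-rho)
- Baseline as covariate: s²(1-rho²)
- Ratio: (1-rho²) / [2(1-rho)] = (1+rho)/2
- Cut in variance: (1-rho)/2, that is 40%, 25%, 10% and 5% at rho 0.2, 0.5, 0.8 and 0.9
- Width ratio, √[(1+rho)/2]: 0.775, 0.866, 0.949 and 0.975

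**Small-sample width.** Multiply by the ratio of t quantiles (N-2-q over N-2 degrees of freedom) and by √[(N-3)/(N-3-q)], where q is the number of covariates. Example with N = 16, rho = 0.5, q = 1: 0.866 × (2.160/2.145) × √(13/12) = 0.908.

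Expected width, adjusted over change score, baseline only (q = 1):

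| N | rho 0.2 | rho 0.5 | rho 0.8 | rho 0.9 |
|---|---|---|---|---|
| 16 | 0.812 | 0.908 | 0.995 | 1.022 |
| 24 | 0.796 | 0.890 | 0.975 | 1.002 |
| 48 | 0.784 | 0.876 | 0.960 | 0.986 |
| 80 | 0.780 | 0.872 | 0.955 | 0.981 |
| 160 | 0.777 | 0.869 | 0.952 | 0.978 |

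Baseline plus both strata (q = 3), with strata assumed to have no prognostic value:

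| N | rho 0.2 | rho 0.5 | rho 0.8 | rho 0.9 |
|---|---|---|---|---|
| 16 | 0.906 | 1.013 | 1.110 | 1.140 |
| 24 | 0.844 | 0.944 | 1.034 | 1.062 |
| 48 | 0.803 | 0.898 | 0.984 | 1.011 |
| 80 | 0.791 | 0.884 | 0.968 | 0.995 |
| 160 | 0.782 | 0.875 | 0.958 | 0.984 |

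Simulation at 5:3 allocation agrees: at rho 0.5, baseline only, the ratio was 0.907 (N = 16), 0.890 (N = 24) and 0.871 (N = 80).

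**Equal variances.** If the follow-up standard deviation is k times the baseline one, the change score has variance s²(1 + k² - 2·rho·k) and the adjusted analysis k²s²(1-rho²). The difference is s²(1 - rho·k)², which is never negative, so in large samples with a common slope adjustment does not lose; only the size of the gain depends on k. In a simulation with a suppressed PDS arm (assumed rho 0.2 and half the standard deviation in PDS, rho 0.7 in the comparator), the baseline-only ratio was 0.70-0.71 for N = 16 to 80, a larger gain than the table shows.

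**The case against.** The strongest reply is that section 5.7.5 describes an exploratory summary with no hypothesis, outside the fixed testing sequence. A simple difference of means is a legitimate choice there, and silence on method is not the same as specifying an unadjusted analysis. Most of this stands. The SAP nowhere says that the comparison is unadjusted; that is only the plain reading, given that it refers to adjusted means where it intends a model. If the method is instead open, the same added sentence is needed.

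Four stronger readings are tempting, and the SAP does not support them:

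- **The subset is small, so the interval is certainly too wide.** No subset size is given. If it is small, the gain depends on rho, and forcing in both strata can widen the interval.
- **The estimate is biased.** Over-correction by a change score is a matter of chance imbalance. No imbalance is shown. If selection made the arms differ systematically, baseline adjustment need not remove the bias and could be the worse choice.
- **Power is lost.** No test or power is planned here, so interval width is the relevant measure.
- **Every other continuous outcome is adjusted.** The adjustment covers those analysed by the mixed model. HbA1c change (5.6.4) and the RetTSQs score (5.7.6.2) are descriptive.

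The reply is also right that the sentence has a prior flaw. A fold change is already relative to baseline, so a change from baseline in it is not well defined, and the variance formula applies only once a scale on which change is a difference, such as the log, is fixed.

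**Conclusion.** The point holds as a modest improvement in precision. Section 5.7.5 names no baseline adjustment, and none is supplied elsewhere. Adjusting for baseline free VEGF would narrow the expected 95% interval by about 9-22% at rho 0.2-0.5 and by about 0-5% at rho 0.8, for N from 16 to 160. At rho 0.9 the result runs from 2% wider to 2% narrower.

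These figures rest on equal variances, a common slope, and assumed values of rho and N. Weak correlation is plausible if treatment suppresses free VEGF, but that too is an assumption. The benefit under imbalance is limited to chance differences; optional sampling, the implant-timing exclusions and grouping by implant timing remain as they are. No primary or key secondary conclusion is affected.

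**What to change.** In section 5.7.5, replace the between-arm sentence with one that fixes both scale and estimator. The outcome is log free VEGF (the scale of the preceding sentence) at Week 28 for PDS and Week 24 for the comparator, analysed by ANCOVA with treatment and baseline log free VEGF. Report the adjusted difference, back-transformed to a ratio of fold changes, with its 95% confidence interval. Add baseline DRSS level and fluid status only if the subset is large enough, by a threshold set before the data are compared by arm.

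The cost is one sentence and one degree of freedom (three if both strata are added). No new data are needed: a change score already requires each patient's baseline and follow-up values. Biomarker analyses are planned only for the final analysis, so the change should be made before then.

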5.7.6 Patient Treatment Experience Assessment

The patients' perspective on their treatment experience will be captured through two questionnaires: the PPPQ and the RetTSQs.

5.7.6.1 PDS Patient Preference Questionnaire (PPPQ)

The PPPQ is a 3-item questionnaire that captures a patient's preference for treatment, the strength of their preference, and the reasons for their preference (Tschosik et al. 2019). The PPPQ will be administered only to patients who have experience with both PDS and intravitreal ranibizumab injections. The PPPQ specifically assesses patient preference for treatment and could demonstrate a benefit of PDS over intravitreal ranibizumab 0.5 mg due to less frequent treatments and the advantage of a refill-exchange over injection. However, due to the nature of the clinical trial, monthly visits are required so study patients will not experience the advantage of less frequent visits.

The endpoint relating to PPPQ is the:

 Proportion of patients who report preferring PDS treatment to intravitreal ranibizumab treatment, as measured by the PPPQ at Week 52.

This will be assessed by summarizing the following descriptively for strength of preference and reasons for preference:

 Proportion of patients who report preferring PDS treatment compared with intravitreal ranibizumab treatment, as measured by the PPPQ at Weeks 52 and 100 among patients in the PDS arm and at Week 112 among patients in the comparator arm who receive the PDS after completing the Week 64 visit Proportion of patients with bilateral disease (simultaneously receiving ranibizumab
via study eye PDS implant and fellow eye intravitreal injection) who report preferring
PDS treatment compared with intravitreal ranibizumab treatment, as measured by
the PPPQ at Week 52 among patients in the PDS arm who receive PDS in their
study eye and intravitreal ranibizumab in their fellow eye

